8.1.3 Efficacy Population

Efficacy analysis population will include all subjects in safety population, with a valid flortaucipir scan assessment [SUVr (quantitative) and/or visual reads (qualitative)].

For flortaucipir SUVr related analyses, any scans deemed to be unquantifiable due to technical reasons will be excluded from analyses.

All analyses involving imaging outcomes will be based on the efficacy population.

8.2 Disposition of Subjects

The enrolled population will be represented in the disposition table. The disposition table will include a summary of the analysis populations, number of completed and discontinued subjects, and the reasons for discontinuation. All percentages will be based on the safety population.

Disposition data will be presented in a listing.

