8 STATISTICAL ANALYSIS

8.1 Analysis Populations

8.1.1 Enrolled Population

The enrolled population will consist of all subjects who signed informed consent and have data captured in the clinical database. Disposition information will be summarized using the enrolled population.

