8.1.2 Safety Population

The safety analysis population will include all eligible subjects who enroll in ¹⁸F-AV-1451-A23 (A23) and have received at least one dose of flortaucipir F 18 injection.

All demographic, baseline and safety endpoints will be using the safety population.

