8.3 Protocol Deviations/Violations

Subjects who entered the study even though they did not satisfy one or more of the inclusion/exclusion criteria will be listed. Deviations/violations from the protocol will be documented, the Avid/contract research organization (CRO) monitor will then be informed and a course of action will be agreed upon.

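### SAP 8.2 tabulates disposition for enrolled subjects but takes every percentage over the smaller safety population, so the completion percentage cannot show loss before injection (minor, reporting only)

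*SAP*

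**What the plan says.** Two places in the SAP name the set that the disposition table describes. Section 8.1.1: "Disposition information will be summarized using the enrolled population". Section 8.2: "The enrolled population will be represented in the disposition table". The definition in 8.1.1 sets no dosing or eligibility condition: "The enrolled population will consist of all subjects who signed informed consent and have data captured in the clinical database".

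Section 8.2 also gives the contents: "The disposition table will include a summary of the analysis populations, number of completed and discontinued subjects, and the reasons for discontinuation". It then fixes the denominator: "All percentages will be based on the safety population". A disposition listing is planned as well.

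The safety population in 8.1.2 is narrower. The definition begins "The safety analysis population will include all eligible subjects who enroll in" the study, and requires that they "have received at least one dose of flortaucipir F 18 injection". Protocol 8.1.1 defines it the same way.

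Nothing in either document restricts the numerators of the disposition table to the safety population, gives a second denominator, or asks for separate rows for losses before and after injection.

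**The concern.** The table describes one set and its percentages are taken over a subset of it. Two kinds of enrolled subject can fall in the gap.

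- **Subjects who leave before injection.** Screening may precede injection by up to 30 days (SAP 6.3). SAP 4.1 has suitability re-checked just before injection and allows eligible subjects to discontinue or withdraw consent. If they are counted as discontinued, they are in a numerator but not in the denominator.
- **Subjects dosed although ineligible.** SAP 8.3 provides for such entrants: "Subjects who entered the study even though they did not satisfy one or more of the inclusion/exclusion criteria will be listed". It does not predict that there will be any. If one is dosed, the eligibility condition in 8.1.2 keeps that subject out of the denominator, while the subject can still be counted as completed or discontinued.

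The primary objective is to pre-screen subjects by scan, so the share of enrolled subjects who reach the scan is basic descriptive information. The completion percentage as planned cannot give it, and rows of the same table can add to more than 100%.

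**Working it through.** The plan states no completion or dropout figure, so there is none to reproduce. The check uses the population definitions and then ratios.

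**Inputs**

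- N = 500 enrolled (SAP 4.5, approximate).
- U = enrolled subjects never dosed. Not given; assumed. All are counted as discontinued.
- V = subjects dosed but ineligible. Not given; assumed. All complete.
- S = N − U − V = safety population (SAP 8.1.2).
- All dosed subjects complete, so completed = N − U.

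**Step 1: the completion row.** Participation runs until the PET scan is completed (SAP 4.1), so a completer has been injected. Undosed subjects are then in neither the numerator nor the denominator of completed/S, whether they are labelled discontinued, screen failure or anything else. With V = 0, completed/S = (N − U)/(N − U) = 100% for every U.

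**Step 2: any row.** A count k prints as k/S = (k/N) × (N/S), so each share of enrolled is inflated by N/S. Completed plus discontinued prints as N/S, which exceeds 100% as soon as U + V > 0.

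**Step 3: numbers.** Printed = over S; share = over N.

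| U | V | S | Completed, printed | Completed, share | Discontinued, printed | Discontinued, share | Sum printed |
|---|---|---|---|---|---|---|---|
| 0 | 0 | 500 | 100% | 100% | 0% | 0% | 100% |
| 10 | 0 | 490 | 490/490 = 100% | 98.0% | 10/490 = 2.04% | 2.00% | 102.04% |
| 25 | 0 | 475 | 475/475 = 100% | 95.0% | 25/475 = 5.26% | 5.00% | 105.26% |
| 50 | 0 | 450 | 450/450 = 100% | 90.0% | 50/450 = 11.11% | 10.00% | 111.11% |
| 100 | 0 | 400 | 400/400 = 100% | 80.0% | 100/400 = 25.0% | 20.0% | 125.0% |
| 200 | 0 | 300 | 300/300 = 100% | 60.0% | 200/300 = 66.7% | 40.0% | 166.7% |
| 0 | 5 | 495 | 500/495 = 101.01% | 100% | 0% | 0% | 101.01% |
| 10 | 5 | 485 | 490/485 = 101.03% | 98.0% | 10/485 = 2.06% | 2.00% | 103.09% |

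**Step 4: which row is more affected.** With V = 0 and u = U/N, the completion row is off by u and the discontinuation row by u/(1 − u) − u = u²/(1 − u). The completion row is off by 1 point at 5 undosed (495/495 = 100% against 99.0%). The discontinuation row stays within 1 point up to 47 undosed (47/453 = 10.38% against 9.40%, 0.98 points) and passes it at 48 (48/452 = 10.62% against 9.60%, 1.02 points). At low rates of loss the distortion is almost all in the completion row.

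The two denominators agree only if every enrolled subject is eligible and dosed.

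**The case against.** The strongest reply is that almost nothing follows from this. The same table must show the size of each analysis population, the completed and discontinued counts and the reasons, and a listing backs it up. A reader can subtract safety from enrolled and see how many subjects fall outside the dosed set. That is correct, and it is why the point is minor: the blindness belongs to the percentage, not to the whole table.

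A second reply is that completion among dosed subjects is a meaningful figure in a one-injection study, and that showing enrolled counts beside percentages of dosed subjects could be deliberate. It would be coherent if the numerators were limited to dosed subjects or the column were labelled that way. The SAP does neither, and it says twice that the table is for enrolled subjects.

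Third, sums above 100% in the cases with V = 0 depend on undosed subjects being tabulated as discontinued. SAP 4.1 supports that label for eligible subjects who withdraw, but nothing settles it for screen failures. This part of the objection stands. So does the point that the dosed-but-ineligible cases arise from the word eligible in the safety definition, and that no such subject may occur. Neither touches step 1 of the working, which holds under any label for undosed subjects.

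**Conclusion.** The concern holds as a minor, reporting-only error. The rule as written gives a completion percentage that carries no information about loss before injection, and rows whose numerators can lie outside their denominator. No imaging or adverse event result is affected.

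The size is unknown. The documents give no rate for undosed or dosed-but-ineligible subjects, so every percentage in the working rests on assumed U and V with N = 500. At 2% to 10% undosed, all counted as discontinued, completion is overstated by 2 to 10 points and discontinuation by 0.04 to 1.1 points. The larger rates in the table matter mainly if screen failures are tabulated, and that is not settled: SAP 8.1.1 asks only for consent and data, while Protocol 5.3.1 uses enrol for patients who meet the criteria.

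**What to change.** In SAP 8.2, replace the sentence on percentages with one stating that every percentage in the disposition table uses the enrolled population as its denominator. This restores the base that SAP 8.1.1 already names for disposition. The cost is one SAP sentence and one table shell, with no protocol change.

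While that sentence is being edited, it would help to say whether screen failures with data count as enrolled, because the new denominator depends on it. If completion among dosed subjects is also wanted, add it as a separate, labelled percentage with its numerator limited to the safety population, and split discontinuations into before and after injection. These additions are optional; the corrected denominator is sufficient to remove the error.

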8.3 Protocol Deviations/Violations

Subjects who entered the study even though they did not satisfy one or more of the inclusion/exclusion criteria will be listed. Deviations/violations from the protocol will be documented, the Avid/contract research organization (CRO) monitor will then be informed and a course of action will be agreed upon.

8.4 Demographic and Other Baseline Characteristics

All baseline summaries will be based on the safety population.

Frequency distributions and summary statistics for demographic and baseline variables will be presented across all subjects. Key demographic and baseline characteristics to be summarized include: age, gender, race, ethnicity, height, weight, BMI, highest level of education, alcohol history, recreational drug use history, smoking history, MMSE, and ApoE Genetic testing.

All demographic and baseline characteristics data will be presented in listings.

8.5 Relevant Family History

Data from Family History CRF will be summarized in a table with counts and percentages and presented in a listing for the safety population.

8.6 Disease History

Months since symptom onset and diagnosis will be summarized in a table using descriptive statistics and presented in a listing for the safety population.

For subjects with dates of diagnosis or symptom onset, months will be calculated as the difference of symptom onset/diagnosis date and the date of their flortaucipir injection.

For partial symptom onset/diagnosis date, if only the day is missing, then impute the day as the first day of the month; if both the day and month are missing, then imputed it as 01 January of the year.

8.7 Pregnancy Test

Data from Pregnancy Test CRF will be presented in a listing for the safety population.

8.8 Concomitant Therapy

A current version of the World Health Organization (WHO) Drug Dictionary will be used to classify medications by preferred term and WHO Anatomical Therapeutic Chemical (ATC) classification of ingredients. ATC classification level 3 will be used. If level 3 is missing, then level 2 will be used. If level 2 is missing, then level 1 will be used.

All concomitant medications data will be presented in listings for the safety population.

8.9 Medical and Surgical History

Medical and Surgical History will be coded using MedDRA Version 21.1. Medical and surgical history will be presented in a listing for the safety population.

8.10 Analysis of Efficacy Parameters

All efficacy information as well as related data (flortaucipir PET scan information and flortaucipir PET results) will be presented in the listings.

8.10.1 Qualitative Assessment of Images

The visual read results will be categorized as τ AD+, τ AD++ and τ AD-. The visual read results will be summarized by frequency distribution (count and percentage) for the efficacy population by subject eligibility and overall.

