**Approval/Signature**

**CONFIDENTIAL**

This material is the property of Avid Radiopharmaceuticals, Inc. (Avid). The information is confidential and is to be used only in connection with matters authorized by Avid and no part of it is to be disclosed to others without prior written permission from Avid.

Sponsor: Avid Radiopharmaceuticals, Inc.	Name of Compound: Flortaucipir F 18 (  F-AV-1451)	Active Ingredient(s): 7-(6-[F-18]fluoropyridin-3-yl)-5H-pyrido[4,3-b]indole
Title of Study:  F-AV-1451-A23 A multicenter screening study with flortaucipir F 18 in patients with early symptomatic AD		
Planned number of subjects (Enrolled): Approximately 500		
Name of compound: flortaucipir F 18 (  F-AV-1451) Dose: 370 MBq (10 mCi) Route of Administration: Intravenous (IV) bolus		
Study Phase: II		
Study Centers: Approximately 15 centers in the United States and Canada		
Trial Objectives:  The primary objective of the protocol is: 
 
To pre-screen patients via a flortaucipir F 18 scan, who have objectively verified cognitive impairment and etiology diagnosed or suspected to be Alzheimer’s disease (AD), and have indicated their interest in participating in Lilly sponsored trials that require tau imaging for inclusion such as I5T-MC-AACG (AACG).
 
 The secondary objective of the protocol is: 
 
To expand the flortaucipir F 18 safety database.
 
		
Eligibility: See Section 5.3, Selection of Patients.		
Study Design:  Study  F-AV-1451-A23 is a multicenter screening study in patients with early symptomatic AD (where early symptomatic AD refers to the combination of 2 stages: prodromal AD [MCI-AD] and mild AD dementia).  All patients will provide informed consent before starting any study procedures. This pre-screening study targets patients who are interested in participating in AD therapeutic clinical trials and have expressed a preliminary interest in a trial like the AACG trial, and who are not known to meet any of the exclusion criteria for trials like AACG based on medical history and clinical examination. However, consent for this protocol does not constitute consent for the		

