4 STUDY DESIGN

4.1 General Design

Study ¹⁸F-AV-1451-A23 is a multicenter screening study in subjects with early symptomatic AD (where early symptomatic AD refers to the combination of 2 stages: prodromal AD [MCI-AD] and mild AD dementia).

All subjects will provide informed consent before starting any study procedures. This prescreening study targets subjects who are interested in participating in AD therapeutic clinical trials and have expressed a preliminary interest in a trial like the AACG trial, and who are not known to have met any of the exclusion criteria for trials like AACG based on medical history and clinical examination. However, consent for this protocol does not constitute consent for the AACG trial or any other trials, and subjects who qualify for this protocol may still fail to qualify for trials like AACG or other trials based on the results of this protocol or based on additional testing performed in those subsequent trials.

Screening assessments may take place over several days and will be performed within 30 days prior to flortaucipir F 18 injection. Screening assessments will include demographic information, cognitive testing, disease history, concomitant medications, vital signs, ECG and medical history. Subjects who are deemed eligible to continue will complete a flortaucipir PET scan.

A physician or a licensed/credentialed medical professional (i.e., a PET technologist, imaging center nurse or a regional equivalent) designated by the site principal investigator must assess or evaluate the subject prior to administration of flortaucipir F 18 injection to determine if they are still suitable to undergo the scan.

All subjects will receive a single IV bolus administration target dose of 370 MBq (10 mCi) of flortaucipir F 18 injection followed by saline flush. At approximately 75 minutes following injection, a continuous 30-minute brain scan will be performed.

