The injection site will be observed for excessive inflammation or damage to the surrounding tissue at the injection site. Adverse events will be continuously monitored during the flortaucipir PET imaging visit. Subjects who experience an adverse event will not be discharged from the imaging center until the event has resolved or stabilized. A follow-up phone call to the subject, or informant where applicable, will be conducted within 2 or 3 business days of the imaging day, but not before 48 hours post-injection, to confirm subject well-being and to collect any new adverse events.

A physician or a licensed/credentialed medical professional (i.e., a PET technologist, imaging center nurse or a regional equivalent) designated by the site principal investigator must assess or evaluate the subject prior to discharge from the imaging center to evaluate the subject's readiness for discharge.

Subjects who meet eligibility criteria will participate in this protocol until they complete their flortaucipir PET scan, or they discontinue, withdraw consent, or if the sponsor decides to end this protocol early.

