8.10.2 Quantitative Assessment of Images

The Screening MUBADA SUV_r will be summarized using descriptive statistics [n, mean, SD, median, minimum and maximum values, and quartiles (25th and 75th percentile)] by visual read results (τ AD+, τ AD++ subject eligibility and overall).

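### The safety population in SAP 8.1.2 is limited to eligible subjects, so a dosed subject who failed an entry criterion drops out of the safety and imaging summary tables

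*SAP*

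**What the plan says.** SAP 8.1.2 opens: "The safety analysis population will include all eligible subjects who enroll in" A23. It adds the condition of at least one dose of flortaucipir and assigns all demographic, baseline and safety endpoints to this population. Protocol 8.1.1 carries the same restriction to eligible patients.

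SAP 8.1.3 builds on it: "Efficacy analysis population will include all subjects in safety population, with a valid flortaucipir scan assessment". It bases every imaging analysis on that set.

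SAP 8.3 covers subjects who should not have entered: "Subjects who entered the study even though they did not satisfy one or more of the inclusion/exclusion criteria will be listed". It gives no rule on their place in the analysis populations.

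The secondary objective, in both documents, is to enlarge the flortaucipir safety database.

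The word also appears in two table specifications. SAP 8.10.1 summarises the visual reads "for the efficacy population by subject eligibility and overall", and SAP 8.10.2 summarises MUBADA SUVr "by visual read results (τ AD+, τ AD++ subject eligibility and overall". Neither says what the subject is eligible for.

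**The concern.** A safety population normally includes everyone exposed, because an adverse event after injection is informative whether or not the subject should have been enrolled. Here an entry-criteria condition sits on top of the dosing condition. A subject who was injected and later found to have failed a criterion, such as the QTcF limit or a prohibited medication, would leave the numerator and the denominator of every safety table. Subjects who failed a medical exclusion criterion are among those a safety database can least afford to omit. Because the efficacy population is nested in the safety population, their scan results would leave the imaging tables too.

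**Working it through.** No figure in the plan needs reproducing, so the check sets the definitions side by side.

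**1. Who is enrolled.** SAP 8.1.1 counts everyone who signed consent and has data in the clinical database. No entry criterion is involved, so this set can contain subjects who failed one.

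**2. What eligible refers to in 8.1.2.** The sentence is about enrolling in A23. The protocol synopsis entry on eligibility says "See Section 5.3, Selection of Patients". Protocol 5.3.2 describes anyone who meets an exclusion criterion as not eligible for enrolment. SAP 4.1 uses the term in the same way: "Subjects who meet eligibility criteria will participate in this protocol until they complete their flortaucipir PET scan". The natural reading is therefore the A23 criteria.

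**3. What the word adds.** Let D be the number of enrolled and dosed subjects, and k the number of those who failed at least one criterion. Screen failures who were never injected are already removed by the dosing condition. So the word has only two possible effects:

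| Reading of eligible in 8.1.2 | Safety population |
|---|---|
| Met all A23 criteria (literal) | D − k |
| Judged eligible by the site at the time | D |

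It either removes exactly the k dosed subjects with a criteria violation, or it does nothing.

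**4. Whether k can be positive.** SAP 8.3 plans a listing for such entrants, so the plan allows for it.

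**5. Effect on the tables under the literal reading.** If a of the D dosed subjects have a given event, b of them among the k, the table shows (a − b)/(D − k) instead of a/D. The same population governs the exposure, vital signs, ECG and baseline summaries, and it is the percentage base for the disposition table (SAP 8.2). If j of the k subjects have a valid scan assessment (j ≤ k), the imaging tables lose those j.

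**6. Size.** The documents give no value for k. With the planned enrolment of about 500, and assuming all are dosed, each such subject is 1/500 = 0.2% of the dosed set. If fewer than 500 are dosed, the share per subject is larger.

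**7. What the listings keep.** SAP 7.1 promises listings of all eCRF data, 8.10 of all efficacy information and 8.11.2 of all adverse events. The records survive there, although 8.11.1 describes the exposure listing as one for the safety population. A listing does not restore a subject to a summary count.

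**8. Subject eligibility in 8.10.** Two meanings are possible:

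| Meaning | Not-eligible row |
|---|---|
| A23 criteria | Always 0 under the literal 8.1.2, because the efficacy set lies inside the safety set, which lies inside the eligible set |
| Suitability for an AACG-type trial | Can be non-zero |

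The study exists to pre-screen for trials that need tau imaging. SAP 4.1 says subjects may fail to qualify for those trials "based on the results of this protocol or based on additional testing performed in those subsequent trials". The second meaning is therefore the likelier one, though the SAP does not state it. It also leaves open whether the decision is the one based on the A23 scan or final qualification after further testing.

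**The case against.** The best defence is that eligible in 8.1.2 means judged eligible at the site. SAP 4.1 says that subjects deemed eligible to continue go on to the scan, and on that view everyone injected was eligible in the operative sense, even if a violation was found later. This reading is possible, and under it no subject is lost. But 8.1.2 does not state it, the protocol's criteria section uses the word for the criteria themselves, and on this reading the word does no work. A programmer deriving a population flag could reasonably go either way.

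It can also be said that nothing is hidden, since the listings hold the events and scans. That is true of the records but not of the counts and percentages, which are what a pooled safety summary would draw on.

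A reader might go further and infer from 8.10 that the not-eligible row is always empty, so that the main pre-screening tables have only one level. The documents do not support that. The empty row arises only if A23 eligibility is meant, and the study's purpose makes suitability for a later trial the likelier meaning. Table shells or eCRF specifications that were not supplied may define the term. What stands there is a missing definition and nothing more.

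**Conclusion.** As written, SAP 8.1.2 and protocol 8.1.1 exclude from the safety population, and through 8.1.3 from the efficacy population, any dosed subject who failed an A23 criterion. SAP 8.3 foresees such subjects and only lists them. The conclusion rests on two assumptions: that eligible is applied literally, and that at least one such subject is dosed. The number affected cannot be derived, and the documents do not show that any subject has been dropped. Every summary is descriptive and no test depends on the population. The effect is limited to who is counted in the tables, but it runs against the stated safety objective and is easy to remove. The undefined term in 8.10.1 and 8.10.2 is a clarification only.

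**What to change.** In SAP 8.1.2 write: *The safety population will include all enrolled subjects who received flortaucipir F 18 injection, whether or not they met every inclusion/exclusion criterion.* Enrolled is already defined in SAP 8.1.1. SAP 8.1.3 then follows without change. Record the departure from protocol 8.1.1 in SAP 5.2, which now states that there are none.

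As a clarification, add one sentence to SAP 8.10 stating which trial subject eligibility refers to, which data field holds it, and whether it is decided on the A23 scan or after later testing. The sponsor must supply these items.

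The cost is one reworded sentence, one entry in 5.2 and one clarifying sentence, with no new scan, read or image processing. If final qualification for another trial is meant in 8.10, that result has to be obtained from that trial. The downside is that any dosed subjects with criteria violations enter the tables. They stay identifiable through the 8.3 listing.
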